Clinical Evaluations: The SCOPA-AUT⁵², a validated questionnaire for autonomic symptoms in PD, and the Orthostatic Hypotension Questionnaire (OHQ)⁵³, a validated questionnaire for symptoms of orthostatic

intolerance, will be administered before, and then by telephone one day after, and four days after each stimulation session. The Beck Depression inventory II (BDI-II)⁵⁴, recommended for screening and assessment of depression severity in PD⁵⁵, will be administered before, and then by telephone one day after, and four days after each stimulation. A trained research team member will administer the Movement Disorders Society Unified Parkinson Disease Rating Scale (MDS-UPDRS)⁵¹, a validated rating scale of PD symptom severity, at baseline. Participants will have orthostatic blood pressure measurement with a standard sphygmomanometer cuff before and after each stimulation session. All evaluations will be done with subjects in the “on” medication state with regards to dopaminergic medication dosing. Quantitative EEG (qEEG) recordings will be done before and immediately after each stimulation session. EEG: A high-density EEG net (128 electrodes including electrooculography electrodes; MagStim EGI, Inc.) and two submental electromyography (EMG) electrodes will be applied. Continuous qEEG recording will be performed for 8 minutes while the participant is asked to keep their eyes open and focused on a crosshairs. Sampling rate during the continuous recording will be 1 kHz with Cz as the reference and a channel between Cz and Pz as ground, using an EGI system with SDK AmpServer Pro (Geodesic, Eugene, Oregon). Intermittent theta-burst stimulation: Subjects will undergo iTBS to the mPFC, left DLPFC, and left primary sensory area in a triple cross-over study design. I will use a MagVenture MagPro X100 TMS device with active cooling coil. Stimulation location will be determined using established scalp coordinates for each stimulation location with the “10-20” international coordinate system⁴²⁻⁴⁵. For the mPFC, stimulation will be done at the Fp1 EEG electrode location, which can be calculated as along the midline of the scalp and 10% of the distance from nasion to inion. For left DLPFC, stimulation will be done at the F3 location using the Beam-F3 technique^{46,47}. For the primary sensory cortex, stimulation will be done 1.5cm posterior to the motor hotspot used for intensity calibration. Stimulation will be delivered at 80% active motor threshold. Accelerated iTBS will be performed in the reclined position to reduce symptoms of orthostatic hypotension, with subjects awake and at rest. Subjects will receive bursts of 3 pulses at 50 Hz repeated at 200-msec intervals (5Hz) for two seconds^{48,49}. The two-second trains will be repeated 20 times every 10 seconds (4 minutes total stimulation time), and followed by a 20 minute rest period. This sequence will be repeated 4 times. Behavioral effects of stimulation last at least 36 hours after one stimulation session with this protocol¹. TMS is FDA-approved for the treatment of symptoms of depression, and is a widely-used safe clinical tool.

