9.1 STATISTICAL HYPOTHESES

Aim 1

H_0 : Mean change in Frontal midline theta power on electroencephalogram after iTBS to the medial prefrontal cortex will be equal to FMT changes after dorsolateral prefrontal cortex stimulation and stimulation of S1.

H_1 : Mean change in Frontal midline theta power on electroencephalogram after iTBS to the medial prefrontal cortex will be greater than FMT changes after dorsolateral prefrontal cortex stimulation and stimulation of S1.

Primary Outcome Measure: The primary objective will test the degree of change in frontal midline theta (FMT) power (μ) before and after iTBS at each stimulation location. The primary outcome measure will be FMT power. *Aim 2a Hypothesis:*

H_0 : There is zero correlation between severity of autonomic dysfunction symptoms at baseline before stimulation with frontal midline theta power at baseline on electroencephalogram.

H_1 : There is a negative correlation between severity of autonomic dysfunction symptoms at baseline before stimulation with frontal midline theta power at baseline on electroencephalogram.

Aim 2b Hypothesis:

H_0 : There is no correlation between severity of depression symptoms at baseline before stimulation with frontal midline theta power on electroencephalogram at baseline.

H_1 : There is negative correlation between depression symptoms at baseline before stimulation with frontal midline theta power on electroencephalogram at baseline.

- Primary Outcome Measures: We will test associations between autonomic symptoms, depression symptoms, and FMT power at baseline before stimulation, where the FMT power (μ) will be the primary outcome measure.

Exploratory objectives

Aim 3 Hypothesis:

H_0 : Change in SCOPA-AUT and OHQ will be zero one day after stimulation and 4 days after stimulation compared to pre-stimulation.

H_1 : Change in SCOPA-AUT and OHQ will be less than zero one day after stimulation and 4 days after stimulation.

- Primary Outcome Measures: Change in SCOPA-AUT and OHQ from before to one day and 4 days after stimulation

Aim 4 Hypothesis:

H_0 : Change in BDI-II will be zero one day after stimulation and 4 days after stimulation compared to pre-stimulation.

H_1 : Change in BDI-II will be less than zero one day after stimulation and 4 days after stimulation.

- Primary Outcome Measure: Change in BDI-II before to one day and 4 days after stimulation

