Primary Analysis, Aim 2: 1. To test associations of autonomic symptoms in PD subjects with FMT, we will use linear regression modeling. The dependent variable will be FMT, whereas primary covariates will be SCOPA-AUT, OHQ score, and magnitude of systolic blood pressure reduction during orthostatic blood pressure measurement. We will further use linear regression models to examine the associations between depression symptoms in PD subjects and FMT, using linear regression modeling. **Exploratory Analyses:** 1. We will use linear mixed models to examine the effect of iTBS on autonomic symptoms one day after, and 4 days after stimulation. SCOPA-AUT and OHQ will be the dependent variable in the ANOVA analysis. The factors will be stimulation location (mPFC, DLPFC, S1) by time (before and after). 2. Similarly, we will use linear mixed models to evaluate the effect of iTBS on depression symptoms one day after, and 4 days after stimulation. BDI-II will be the dependent variable, whereas the primary factors will be stimulation location (mPFC, DLPFC, S1) by time (before and after). **In all statistical models,** Some key confounding factors (age, disease duration) will be controlled in both linear mixed effects and regression models. **Post-hoc analysis** will be performed using Tukey's method to control for multiple comparisons.

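### Exploratory Aims 3 and 4 concern effects at day 1 and at day 4, but the model's time factor has only two levels (before, after) and the plan does not say how the two follow-up readings enter it

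*Combined protocol and SAP*

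**What the plan says.** Section 9.1 defines the Aim 3 outcome as "Change in SCOPA-AUT and OHQ from before to one day and 4 days after stimulation" and the Aim 4 outcome as "Change in BDI-II before to one day and 4 days after stimulation". The Aim 3 alternative hypothesis is directional and names both times: "Change in SCOPA-AUT and OHQ will be less than zero one day after stimulation and 4 days after stimulation". Aim 4 has the same form for BDI-II.

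The data match the hypotheses. Section 6.1.2 says the autonomic questionnaires "will be administered before, and then by telephone one day after, and four days after each stimulation session", and BDI-II follows the same timing. The Schedule of Activities (1.3) and section 8.1.1 agree. That is three readings per session on each scale.

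Section 9.4.1 first gives the purpose of the Aim 3 model: "We will use linear mixed models to examine the effect of iTBS on autonomic symptoms one day after, and 4 days after stimulation". It then gives the design: "The factors will be stimulation location (mPFC, DLPFC, S1) by time (before and after"). For depression it repeats the pattern: "BDI-II will be the dependent variable, whereas the primary factors will be stimulation location (mPFC, DLPFC, S1) by time (before and after"). Section 9.4.3 only refers back to 9.4.1. No day-1 or day-4 contrast is named anywhere.

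**The concern.** The stated purpose of the model and its stated time factor do not fit together. A two-level factor suits Aim 1, where EEG is recorded once before and once immediately after stimulation. Aims 3 and 4 have two post-stimulation readings. With two levels, both readings fall under one after level, and the fitted interaction is a single averaged change per location. The planned Tukey comparisons act on the levels a model contains, so they cannot recover a day-1 or day-4 effect.

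If the effect differs between the two calls, the pooled figure understates the larger effect and overstates the smaller one. The time course, which is what two calls can show, would not be reported. Since the text allows more than one reading, the choice could also be made after the data are seen.

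**Working it through.** **1. The plan's own figure.** Section 9.2 gives exploratory power of 0.95 (0.26 to 1.00) from g = 1.0 (0.3 to 1.7), N = 45, alpha 0.05 and two predictors. Take f² = g²/4, noncentrality = √(f²N) and df = 45 − 2 − 1 = 42, and test one coefficient one-sided.

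- g = 1.0: f² = 0.25, noncentrality √11.25 = 3.35, power 0.951.
- g = 0.3: power 0.256.
- g = 1.7: power 1.000.

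All three figures reproduce. At g = 1.0 a two-sided test gives 0.906 and the omnibus F gives 0.834, so the stated power is one-sided. The calculation has no day-1/day-4 component and does not show which time coding was intended.

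**2. What literal pooling does.** Assumptions: equal variance s² and equal correlation r among the three readings (compound symmetry, as implied by the random intercept that 9.4.1 offers alongside AR(1)); effect d at day 1 and k·d at day 4.

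- Day-1 change: estimate d, variance 2s²(1 − r).
- Mean of both follow-ups minus before: estimate d(1 + k)/2, variance 1.5s²(1 − r).
- SE ratio: √(1.5/2) = 0.866.
- Standardised effect, pooled relative to day 1: [(1 + k)/2]/0.866 = 0.577(1 + k).

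For k = 0 (no effect left at day 4) the estimate is d/2 and the ratio is 0.577. Power when the day-1 contrast alone would have 80% or 90%:

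- Two-sided, 80%: Φ(0.577 × (1.960 + 0.842) − 1.960) = Φ(−0.34) = 0.37.
- Two-sided, 90%: Φ(0.577 × (1.960 + 1.282) − 1.960) = Φ(−0.09) = 0.46.
- One-sided, 80%: Φ(0.577 × (1.645 + 0.842) − 1.645) = Φ(−0.21) = 0.42.
- One-sided, 90%: Φ(0.577 × (1.645 + 1.282) − 1.645) = Φ(0.04) = 0.52.

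The documents give no decay, so k should be varied:

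| Day-4 effect as a fraction of day 1 (k) | Pooled estimate | Standardised ratio | Power from 80%, two-sided |
|---|---|---|---|
| 0 | 0.50d | 0.577 | 0.37 |
| 0.5 | 0.75d | 0.866 | Φ(0.866 × 2.802 − 1.960) = 0.68 |
| 0.73 | 0.87d | 1.00 | 0.80 |
| 1 | d | 1.155 | Φ(1.155 × 2.802 − 1.960) = 0.90 |

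With equal effects, pooling is unbiased and more precise. It loses power for day 1 only when the day-4 effect is below about 73% of the day-1 effect.

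**3. Simulation check.** Location-by-time model with subject intercepts, N = 48, 4,000 runs, residual SD 1 with independent errors (assumed), and an mPFC-only effect at day 1 that is zero at day 4. The contrast is mPFC versus S1, one-sided.

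| True day-1 effect | Three levels: day 1, day 4 | Power, day 1 | Two levels: single contrast | Power |
|---|---|---|---|---|
| 1.0 SD | 1.00, 0.00 | 0.96 | 0.50 | 0.61 |
| 0.5 SD | 0.50, 0.01 | 0.53 | 0.25 | 0.26 |

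The simulation confirms the halving. A large transient effect is often still detected under pooling, but at half its size and with no day attached.

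**The case against.** The strongest reply is that pooling is nowhere stated. The sentence before the factor definition says the models examine the effect at one day and at four days, and section 9.4.1 speaks of repeated measures over time. A before/after model for each follow-up day, or loose shorthand for three levels, would fit those words, and either would estimate both named effects. This stands: a reader might infer that the plan has decided to average the two days, and the documents do not support that. What remains is that the factor as written contradicts its stated purpose.

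A reader might also infer that a day-1 effect would be averaged away. It would not: with no effect left at day 4 it is halved.

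Third, it is tempting to argue from "Behavioral effects of stimulation last at least 36 hours after one stimulation session with this protocol" that day 4, at about 96 hours, lies beyond the effect. That figure is a lower bound and does not show extinction. The synopsis allows three weeks for physiologic effects to return to baseline, and the alternative hypotheses expect a reduction at both times. The protocol therefore gives no ground for assuming that the effect is gone by day 4, and none for assuming that it is equal on the two days.

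Finally, these are exploratory aims in a pilot study, and all three readings are collected, so a separate analysis stays possible. That limits the consequence but does not settle which analysis is planned.

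**Conclusion.** The point holds as a contradiction within section 9.4.1: two named effect times, three readings per session, and a two-level time factor. Taken literally, the model does not estimate the Aim 3 and Aim 4 hypotheses in section 9.1. Other readings would, and the plan does not choose between them.

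The size depends on assumptions outside the documents. With literal pooling, compound symmetry and a day-4 effect of exactly zero, the estimate is d/2, the standardised effect is 58%, and 80% power becomes about 37% two-sided or 42% one-sided. That is the unfavourable end for an effect that fades to nothing; the loss shrinks as the day-4 effect approaches the day-1 effect, and with equal effects there is no bias. Aim 1 has only two times and Aim 2 uses baseline data, so no primary result is touched. The plan should be corrected, but this does not threaten its main conclusions.

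**What to change.** In section 9.4.1, for Aims 3 and 4, replace the two-level time factor with a three-level categorical factor (pre-stimulation, day 1, day 4) in the location-by-time model for SCOPA-AUT, OHQ and BDI-II. Prespecify the day-1-versus-pre and day-4-versus-pre contrasts by location. The average of the two follow-up days may be kept as a labelled summary, since it is the more precise quantity if the effect is stable.

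The cost is about one sentence of text, with no new data, visits or participants. The small downside is two contrasts per scale instead of one. Tukey adjustment is already planned for post-hoc comparisons, and the aims are exploratory.

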3 OBJECTIVES AND OUTCOME MEASURES

OBJECTIVES	Outcome Measures

Primary
 
Aim 1: To determine whether iTBS to the medial prefrontal cortex (mPFC) produces more robust changes in frontal midline theta (FMT) EEG power in people with Parkinson's disease compared with stimulation at the dorsolateral prefrontal cortex (DLPFC) or the primary sensory cortex (S1). Aim 2: A. To evaluate FMT power correlations with burden of autonomic symptoms at baseline before stimulation in Parkinson's disease. B. To evaluate FMT power correlations with burden of depression symptoms at baseline before stimulation in Parkinson's disease
	
Aim 1: Degree of change of frontal midline theta power on EEG after brain stimulation. Aim 2: Degree of association between autonomic symptoms and frontal midline theta EEG power; Degree of association between depression symptoms and frontal midline theta EEG power.

Exploratory
 
Aim 3: To evaluate the effect of iTBS on autonomic symptoms one day after, and 4 days after stimulation. Aim 4: To evaluate the effect of iTBS on depression symptoms one day after, and 4 days after stimulation.
 
Aim 5: To create a database of EEG and TMS data in people with PD for
	
1. Change in SCOPA-AUT and OHQ from before to after iTBS; 2. Change in BDI-II from before to after iTBS

OBJECTIVES	Outcome Measures
the purpose of future research into novel neurostimulation therapies for PD NMS	

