9.2 SAMPLE SIZE DETERMINATION

Aim 1: There is no preliminary data for effect size estimation using the paradigm and patient population suggested in this study. The primary outcome measure in aim 1 is change in FTM.

H_0 : Mean change in Frontal midline theta power on electroencephalogram after iTBS to the medial prefrontal cortex will be equal to FMT changes after dorsolateral prefrontal cortex stimulation and stimulation of S1.

H_1 : Mean change in Frontal midline theta power on electroencephalogram after iTBS to the medial prefrontal cortex will be greater than FMT changes after dorsolateral prefrontal cortex stimulation and stimulation of S1.

I expect a medium effect size of $f^2 \geq 0.15$. With significance level set at $\alpha = 0.05$, using linear multiple regression modeling in G*Power software, with 3 predictors, an N of 45 subjects yields power of 0.82 for this crossover design. In a published study examining theta power using EEG plus iTBS at the dorsolateral prefrontal cortex in healthy adults, they found significant changes in theta power after iTBS with an N of 10 subjects⁵⁹. Therefore we propose 48 subjects for this current study, which should sufficiently power our study for the primary outcome measures.

Aim 2: Though there is no preliminary data for theta band power correlates of depression or autonomic symptoms in Parkinson's disease, there are studies that have looked at EEG spectral power correlations of cognitive symptoms in PD. In one study that contained sufficient published data to calculate power, they found a correlation between EEG spectral power and executive dysfunction in PD with an OR of 0.130 (95% CI [0.02-0.83])⁶⁰. The primary outcome measure in Aim 2a and Aim 2b is FTM. I used G*Power software to calculate sample size for a linear regression model with a significance level set at $\alpha = 0.05$ and Power = 0.80, which yielded a necessary sample size of 22 subjects. 45 subjects yields a power of 0.98 (95% confidence interval [0.24 – 0.99]). We will propose to recruit 48 subjects to ensure that our study is sufficiently powered.

Aim 2a:

H_0 : There is zero correlation between severity of autonomic dysfunction symptoms at baseline before stimulation with frontal midline theta power at baseline on electroencephalogram.

H_1 : There is a negative correlation between severity of autonomic dysfunction symptoms at baseline before stimulation with frontal midline theta power at baseline on electroencephalogram.

Aim 2b:

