9.4 STATISTICAL ANALYSES

9.4.1 GENERAL APPROACH

All data are double entered by independent keyboard operators, compared to identify discrepancies, then reconciled with the data manager. All datasets are backed up daily. Linear mixed models with repeated measures across different regions or over time will be the primary analytic tool for testing our *a priori* hypotheses. To model correlation among repeated measures, we will primarily consider either random intercept or AR(1). We will use the likelihood ratio test (or Wald test) statistic to test

the hypotheses. We will appropriately handle missing data (e.g., missing responses and/or covariates) by using imputation or other methods. To identify significant component terms in each of the models, we will examine the parameter estimates, 95% confidence intervals, and p-values of the component terms in an analysis of fixed effects for the final mixed models. Before undertaking statistical modeling, we will perform descriptive analyses and examine the distributions of all measures. Appropriate transformations or nonparametric statistical tests will be considered if necessary. **All statistical estimates of population parameters will be tabulated along with corresponding confidence intervals (CIs) and/or standard errors (SEs) to convey levels of precision / imprecision.** Following is a detailed plan for testing each hypothesis and the power assessment when feasible.

Descriptive statistics: Categorical data (sex) will be presented as percentages. Continuous data (age, disease duration, scores on SCOPA-AUT, OHQ, BDI-II, MDS-UPDRS all parts, freezing of gait questionnaire, Epworth Sleepiness scale, REM sleep behavior disorder questionnaire, and MoCA, will be presented as means with standard deviation and range.

Primary analysis, Aim 1: To test the degree of change in the power of FMT before and after iTBS at each location, we will use linear mixed models with FMT being the dependent variable. We will primarily include stimulation location (mPFC, DLPFC, S1), time (before, after stimulation), and the interaction term Location*time in the model.

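### Aim 1 has no planned contrast, and the only pairwise rule, Tukey's all-pairs method, is valid but poorly matched to H1 and costs power

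*Combined protocol and SAP*

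**What the plan says.** **Hypotheses.** Section 9.1 (repeated in 4.1 and 9.2) states the Aim 1 alternative as mean theta change after mPFC stimulation that "will be greater than FMT changes after dorsolateral prefrontal cortex stimulation and stimulation of S1". The null is that it "will be equal to FMT changes after dorsolateral prefrontal cortex stimulation and stimulation of S1". The objective in Section 3 is looser: it speaks of more robust change at mPFC "compared with stimulation at the dorsolateral prefrontal cortex (DLPFC) or the primary sensory cortex (S1".

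**Model and test.** The Section 9.4.1 mixed model has location, time and "the interaction term Location*time in the model". On testing it says: "We will use the likelihood ratio test (or Wald test) statistic to test" the hypotheses. Estimates, confidence intervals and p-values of the component terms are also to be examined. No reference location is named and no contrast is tied to H1.

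**Multiplicity.** After the models for all the aims, Section 9.4.1 says that post-hoc analysis "will be performed using Tukey's method to control for multiple comparisons". The family of comparisons is not defined. Section 9.4.2 only refers back to 9.4.1.

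**Level and roles.** Section 9.2 sets alpha at 0.05 without stating sidedness and makes no allowance for multiplicity. The synopsis calls mPFC the experimental site, DLPFC an alternative experimental site and S1 the control site.

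**The concern.** The Location*time test has 2 degrees of freedom and no direction. It can be significant because DLPFC differs from S1, or because mPFC gives the smallest change. Only the comparisons of mPFC with each other site can carry the Aim 1 claim, and Tukey is the only rule the plan gives for comparing pairs.

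Tukey protects all three pairs of sites, including DLPFC against S1, which no hypothesis addresses. It is also a two-sided procedure, whereas H1 is directional. If H1 means that mPFC must beat both sites, the joint claim is an intersection-union test: it is false only if at least one component null is true, so testing each component at level alpha already keeps the joint error at or below alpha. On that reading, the Tukey adjustment buys protection the claim does not need and pays for it in power.

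**Working it through.** **1. The plan's own power figure.** Section 9.2 gives power 0.82 with N = 45, f² = 0.15, alpha 0.05 and 3 predictors.
- Single regression coefficient: df = 45 − 3 − 1 = 41, noncentrality = √(0.15 × 45) = √6.75 = 2.598.
- One-sided 0.05: critical t 1.683, power 0.819. This reproduces 0.82.
- Variants that do not reproduce it: two-sided coefficient 0.718; 2-df increment F test 0.604; 3-df overall test 0.528.

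The stated figure is therefore that of one unadjusted, one-sided test.

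**2. Critical values at the planned size.** Inputs: 48 participants (Section 9.2) and three sites. Assumed: all complete, df = 2 × (48 − 1) = 94 for change scores, two-sided 0.05.
- Unadjusted: t(0.975; 94) = 1.99.
- Tukey: q(0.95; 3, 94)/√2 = 3.368/1.414 = 2.38, a two-sided per-pair level of 0.019.

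**3. Power cost.** The documents give no SD or within-person correlation for theta change, so the effect is set by assumed unadjusted per-contrast power. Both contrasts have the same true effect. They share mPFC, so their estimates correlate at 0.5. Results are from simulation; a contrast counts only if mPFC is the larger.

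| Claim | Unadjusted | Interaction test first, then unadjusted | Tukey |
|---|---|---|---|
| One named contrast (80% case) | 80% | 75% | 67% |
| Both contrasts (80% case) | 69% | 68% | 53% |
| At least one (80% case) | n/a | 83% | 82% |
| One named contrast (90% case) | 90% | 88% | 81% |
| Both contrasts (90% case) | 83% | 83% | 71% |

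For both contrasts in the 80% case, independent runs gave 52% to 53% under Tukey.

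**4. The same comparison on the plan's effect size.** Carrying f² = 0.15 to each contrast is a further assumption (N = 45, df 41, noncentrality 2.598).

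| Rule | Critical t | Per contrast | Both |
|---|---|---|---|
| Unadjusted, one-sided 0.05 | 1.68 | 0.82 | 0.72 |
| Dunnett over two, one-sided | 1.97 | 0.73 | 0.60 |
| Unadjusted, two-sided 0.05 | 2.02 | 0.72 | 0.58 |
| Tukey, three pairs | 2.43 | 0.57 | 0.41 |

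The joint power falls by 0.72 − 0.41 = 0.31 (0.30 before rounding). About 0.13 of that comes from moving to two-sided tests (0.72 to 0.58) and about 0.17 from the three-pair adjustment (0.58 to 0.41).

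**5. Error rates.**
- *Both required.* The worst case is mPFC equal to one site and far above the other. The false joint claim rate is 2.5% with two-sided 0.05 tests, 5.0% with one-sided 0.05 tests and 1.0% with Tukey. None exceeds 5%.
- *Either suffices, no gate, no adjustment.* With all sites equal, the error is 9.1% two-sided and 8.7% one-sided, so an adjustment or an ordering is needed.
- *Significant interaction test first, then unadjusted pairs.* With three sites, familywise error is about 5% under the global null and when one site differs from two equal ones.

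**The case against.** The plan does not name Tukey as the Aim 1 test. The hypotheses are to be tested by likelihood ratio or Wald, and Tukey is attached to post-hoc work in a sentence that serves every model. The component terms are also to be examined. With mPFC as reference level, the two interaction coefficients are exactly the two required contrasts, unadjusted. All-pairs comparison is defensible where DLPFC is an alternative experimental site and where the hypotheses for Aims 3 and 4 single out no site. This is also a pilot study.

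Much of this stands. Tukey does not inflate error, and calling it wrong would go too far. Nor do the documents support saying that the plan will declare a true mPFC advantage unsupported, because no text makes Tukey decisive for H1. But the reference level is not named, no other pairwise rule is given, and the pairwise step still has to carry the directional claim.

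A reader might also infer that H1 never needs adjustment. That holds only if both contrasts are required. The objective says one or the other, and the null of joint equality is false if either differs. Step 5 shows what unadjusted testing costs on that reading.

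Finally, Tukey run on the six location-by-time means would have a critical t of 2.87 (235 df assumed) and would compare cell means, not changes. The plan does not say it will be used that way, so this is not a measured cost of the plan.

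**Conclusion.** The concern holds as one of mismatch and missing specification. No contrast, sidedness or success rule is fixed for Aim 1, and the one pairwise rule covers a comparison that H1 does not make.

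If both contrasts must succeed, Tukey costs about 16 percentage points of joint power when each has 80% unadjusted power (69% to 53%), and about 12 at 90% (83% to 71%). For one named contrast, the fair comparator is the gated procedure, which controls familywise error. The loss is then about 8 points (75% to 67%), not the 13 suggested by setting 80% against 67%. For a claim of at least one win there is almost no loss (83% to 82%).

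These figures rest on 48 complete participants, 94 df, two-sided tests and equal effects on the two contrasts. The size of the effect is assumed, since the plan supplies no variance for theta change. This is a worthwhile, cheap improvement; it is not an error that invalidates the analysis.

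**What to change.** For Aim 1, replace the Tukey sentence in Section 9.4.1 with two planned difference-in-change contrasts from the mixed model, mPFC−S1 and mPFC−DLPFC, and state whether they are one- or two-sided. Then reconcile the objective with H1 and write down one success rule:

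- **Both required (H1 as worded):** test each contrast at the full 0.05; H1 is supported only if both are significant in favour of mPFC.
- **A single-contrast claim counts:** test mPFC−S1 first and mPFC−DLPFC only if it succeeds, each at 0.05; or apply Holm or Dunnett over the two contrasts.

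Report DLPFC−S1 descriptively with a 95% confidence interval. Tukey can stay for the exploratory all-pairs comparisons in Aims 3 and 4. Restate the Section 9.2 power for the chosen rule and sidedness, since 0.82 describes one unadjusted one-sided test.

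The cost is SAP wording, with no new data or visits. The one thing given up is any confirmatory claim about DLPFC against S1, and the hypotheses make none.
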